Florajen3, currently used in Marquette University's clinical trial, is no longer manufactured. Therefore, for our research we will use Florajen Digestion as the intervention. Compared with Florajen3, Florajen Digestion has two additional probiotic species. Florajen Digestion is a probiotic combination product composed of freeze-dried strains of live organisms, including Howaru® Dophilus-*Lactobacillus acidophilus* NCFMTM; *Lactobacillus acidophilus* La-14; floraFIT *Bifidobacterium lactis* Bi-07TM; *Bifidobacterium animalis* ssp. Lactis HN019, floraFIT *Bifidobacterium longum* Bl-05TM for a total 15 x10⁹ CFU per capsule. In vitro testing (Ephraim et al., 2012; Appendix A.2.) demonstrated that the live culture, freeze-dried, probiotic combination Florajen3 inhibited GBS when they are cultured together. In vivo pilot testing of Florajen3 was completed in early 2012 in an open-label, randomized control trial study with 10 pregnant women taking the probiotic capsule daily and 10 serving as controls (Hanson et al., 2014; Appendix A.1.). Findings suggested that the probiotic intervention suppressed growth of GBS. Women in the probiotic group reported no side effects.

IND application for Florajen Digestion was submitted to the FDA in late May 2020 and has been granted (IND # 22834). We have received a commitment letter from the producers of the Florajen Digestion to provide the probiotic product for our research study at no cost.

Page 8 of 31 Version Date: 12/2/2021

3. Study Design

This is an open-label randomized control trial and feasibility of a larger RCT in our setting that would examine prenatal probiotic use in Group B Strep (GBS) positive pregnant women at term. We hope to address the question of whether prenatal oral probiotic use, taken by healthy low risk GBS positive women from approximately 37 weeks gestation until the time of birth, will reduce the number of women who test positive for GBS at the time of admission to Labor and Delivery (L&D). In this study we aim to determine whether such a study is acceptable in our population, whether any adverse events are identified, and what barriers or confounding variables might exist to probiotic use at term. We will also look at whether probiotic use had any reported effect on maternal gastrointestinal (GI) symptoms.

4. Inclusion and Exclusion Criteria

Inclusion Criteria

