Page 10 of 31 Version Date: 12/2/2021

complete the study.

6. Study Timelines

Procedures and Timing: Data will be collected for all subjects at five time points: T1 baseline (36.0-37.6 weeks), T2 (on labor admission), T3 (postpartum day 0-14), T4 (2 weeks postpartum), and T5 (6 weeks postpartum) as indicated in the table below.

Following informed consent, participants will have their first study visit at 36.0-37.6 weeks gestation (T1), during which baseline data will be collected and each subject will complete several brief questionnaires. Participants will be randomized into intervention group or routine care. The research staff member will sequentially distribute one prelabeled bottle of 30 probiotic capsules to the intervention group at time of enrollment. The bottle number will be used as the subject's number for the remainder of the study. Subjects in the control group will not receive any capsules and will be advised to continue their routine prenatal self-care. All subjects in the intervention group will be instructed to keep the study bottle in the refrigerator and to take one capsule per day until they give birth and to bring the bottle with them to the hospital at the time of labor. The PI, co-investigators, research staff, prenatal providers, and the subjects will not be blinded to group assignment.

The GBS vaginal to rectal swab collection procedure will be repeated for the both the intervention and routine care groups at T2 on labor admission. All participants will receive routine IAP per protocol as per CDC guidelines. At T3, the research staff will complete data collection with every participant during postpartum days 0-14; this will involve counting any remaining capsules in the study bottle, administering the study questionnaires, providing each subject with the first thank you merchandise card, and conducting a record review to document birth characteristics and IAP treatment. Adverse events will be solicited at each prenatal visit and via formal questionnaire for participants at T3-T5. Adverse events will be solicited at each prenatal visit and via formal questionnaire at T4-T5 for the newborn(s). A second merchandise card will be provided at T5.

Page 11 of 31 Version Date: 12/2/2021

Summary of Study Data Collection, Variables, Measures, and Timing

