Secondary outcomes include intervention adherence, maternal gastrointestinal (GI)

Page 14 of 31 Version Date: 12/2/2021

symptoms, and maternal and infant adverse events, at the 6 week postpartum visit.

8. Research Setting

The study will be performed at the University of New Mexico (UNMH) Women's Care Clinic, Women's Health Clinic, First Choice Community Healthcare clinics, and Maternity and Family Planning Clinic. Potential subjects will be screened and recruited in the UNMH clinics. After recruitment, they will undergo the consent process, and fill out initial questionnaires in the outpatient offices or over the phone. Upon labor admission to L&D, a GBS swab will be taken for study participants in addition to what is routinely collected for standard of care. There will be no involvement of any community advisory board. There will not be any research conducted outside of the UNM HSC.

9. Resources Available

[name], CNM fills a leadership role in the Department of OBGYN as the Associate Chief of the Midwifery Division. She has completed a Master's in Public Health and has conducted a successful research project, submitted through the UNM IRB This study resulted in a published manuscript in the Journal of Midwifery and Women's Health. In addition, the topic of this current research project was her Master's Thesis work for her Masters of Science in Nursing. She regularly lectures at the College of Nursing on the topic of GBS. [name], CNM will serve as a co-investigator for the current study. As a member of the Midwifery Division, [name] has collaborated on various studies including her role as co-investigator for the UNM APPLE study. She also collaborated on a recent study with Tricore lab, and has an excellent working relationship with the lab, who will work with us on this study. The other UNM co-investigators are part of the Midwifery Division and have collaborated on various studies with the OBGYN Department and Midwifery Division. We will also use the assistance of a medical student on our research team, who has participated in research studies in the past.

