Participant flow through the study: Healthy adult pregnant women, who are GBS positive, at \geq 36 weeks gestation, will be introduced to the study. If they express an interest in the study, the research coordinator will conduct a prenatal chart review after their GBS swab result has returned and review study inclusion and exclusion criteria for each interested woman by completing the Prenatal Eligibility Screening Form (PESF). For a woman who is eligible and willing, the research coordinator will complete the informed consent. Participants will provide written or e-signed consent at 36.0 to 37.6 weeks gestation. Consented participants will be randomized to one of two groups, standard of care/control group or the intervention group. Participants in the intervention group will begin taking oral study capsules once daily from time of enrollment/randomization at \geq 36 weeks gestation until the time of birth. The research staff member will sequentially distribute the pre-labeled bottles of study capsules to the intervention group, one bottle of 30 Florajen Digestion probiotic capsules to women in the intervention group at the time of randomization. Because women are seen on a

Page 16 of 31 Version Date: 12/2/2021

weekly basis in late pregnancy, generally we anticipate that participants will receive the probiotic at enrollment; their next regularly scheduled prenatal appointment at approximately 37 weeks gestation. For women who do not attend this appointment in person, research staff can also arrange to meet participants at the prenatal clinic site to initiate the intervention between prenatal appointments. This will be arranged at the woman's convenience. Subjects in the control group will not receive any capsules and will be advised to continue their routine prenatal self-care. All subjects in the intervention group will be instructed to keep the study bottle in the refrigerator and to take one capsule per day until they give birth and to bring the bottle with them to the hospital at the time of labor.

All participants will complete baseline forms: Antepartum Gastrointestinal Symptom Assessment (AP-GI-SA-10), Demographic Questionnaire and the Questionnaire for Participants.

Research coordinators will be filling out a Summary Data Collection Form (SDCF) on all study participants.

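### The plan starts capsules at randomisation but lets an intervention woman be randomised before she has any, with no limit on the wait and no record of when she starts

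*Combined protocol and SAP*

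**What the plan says.** Several statements tie the capsules to allocation. Section 12 (Study Procedures) says intervention women "will begin taking oral study capsules once daily from time of enrollment/randomization" and that staff distribute "one bottle of 30 Florajen Digestion probiotic capsules to women in the intervention group at the time of randomization". Section 6 (Study Timelines) has staff give out one "prelabeled bottle of 30 probiotic capsules to the intervention group at time of enrollment". Section 3 (Study Design) instead describes use "from approximately 37 weeks gestation until the time of birth", although women may enter from 36.0 weeks.

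Section 12 then adds that receipt is generally expected at the next routine visit, at about 37 weeks, in a sentence that seems to equate this visit with enrolment. For women who do not come to it in person, "research staff can also arrange to meet participants at the prenatal clinic site to initiate the intervention between prenatal appointments", at a time that suits the woman. The wording is permissive and sets no latest date.

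The steps before this need no physical contact:

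- Section 8 lets women "fill out initial questionnaires in the outpatient offices or over the phone", and Section 16 also provides for questionnaires by phone.
- Section 20 has the coordinator telephone with the eligibility result and then obtain consent electronically. Section 26 gives reduced in-person contact as the reason for e-consent.
- Section 12 randomises women once they have consented. Section 16 has a coordinator make the assignment through REDCap.

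Adherence is measured by one final capsule count at postpartum day 0-14 (Sections 6 and 12). The data-collection table in Section 6 lists neither a handover date nor a first-capsule date.

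**The concern.** Taken together, these sections describe two sequences. In one, allocation and capsules arrive together. In the other, allocation can come first and capsules later. The plan does not say that randomisation is held back for women on the second path.

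Three things are at stake.

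- **Exposure.** Time from enrolment to labour is short, so a wait of days takes a noticeable share of it, and only in the intervention arm. This pulls the primary comparison (GBS status at labour admission) towards no difference.
- **Balance after randomisation.** An intervention woman allocated without a bottle has one more step to complete, while a control woman has none. Section 15 allows withdrawal for not following the protocol. It does not say how women who were randomised but have not started are handled, and neither does Section 13.
- **Adherence.** This is a named secondary outcome and a possible covariate in Section 13. A count of capsules left gives the number taken, but not the number of days on which one could have been taken.

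**Working it through.** **1. Does any text close the gap?** Set out in order, the plan gives consent (may be electronic), baseline forms (may be by phone), REDCap assignment (no place or visit specified) and bottle handover. Handover is at randomisation, at enrolment, at the next visit at about 37 weeks, or at a separate clinic meeting. No section makes assignment conditional on a bottle being at hand, limits the delay, or records when it ends. Randomisation before capsules is therefore permitted.

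**2. The plan's own figure.** Section 5 expects about 50 completers from up to 75 enrolled with 30% dropout: 75 × (1 − 0.30) = 52.5, consistent with its approximate figure. The point does not depend on this. It only supplies about 25 per arm for step 5, assuming equal allocation, which the plan does not state.

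**3. Exposure lost to a wait.** Share lost = wait ÷ days from randomisation to birth. Assumed: randomisation at 37+0 and birth at 39+0 (14 days) or 40+0 (21 days). Seven days is the weekly visit interval in Section 12; three days is a shorter case.

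| Days available | 3-day wait | 7-day wait |
|---|---|---|
| 14 | 3/14 = 21% | 7/14 = 50% |
| 21 | 3/21 = 14% | 7/21 = 33% |

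The range is 14% to 50%. At the edge of the entry window (37+6, birth at 39+0) only 8 days are available, so a 3-day wait removes 3/8 = 38% and a 7-day wait 7/8 = 88%.

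**4. Capsule count.** The plan states no denominator. Suppose a woman with 21 days from randomisation to birth waits 7 days and then takes every capsule. She takes 14. Counted from handover, adherence is 14/14 = 100%; counted from randomisation it would be 14/21 = 67%. With a 3-day wait the second figure is 18/21 = 86%. Without a handover date the two cannot be told apart. For scale, the pilot adherence contrast quoted in Section 2 is 68% against 90%, or 22 points.

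**5. What if some women never start?** No rate is given, so this is purely a what-if. It borrows the positive trial summarised in Section 2, in which 21/49 and 9/50 became GBS negative. That gives GBS-positive proportions of pT = 1 − 21/49 = 0.571 and pC = 1 − 9/50 = 0.82. If a fraction f never starts and behaves like controls, pT(f) = pT + f(pC − pT). At f = 0.10 this is 0.571 + 0.10 × 0.249 = 0.596.

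Power = Φ{[Δ − 1.96√(2p̄(1−p̄)/n)] ÷ √([pC(1−pC) + pT(f)(1−pT(f))]/n)}, where Δ = pC − pT(f), p̄ is the mean of the two proportions, n = 25 per arm, and two-sided 0.05 is assumed.

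| f | Δ | Power |
|---|---|---|
| 0 | 0.249 | 47.9% |
| 0.05 | 0.236 | 44.5% |
| 0.10 | 0.224 | 41.0% |
| 0.20 | 0.199 | 34.3% |

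Shortened rather than absent exposure cannot be turned into a power loss, because the documents give no relation between duration and effect.

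**The case against.** The strongest reply is that the gap may be one of wording only. Section 12 says the bottle is given at randomisation, which can mean that randomisation waits for the bottle, and it appears to treat enrolment and the next visit as one event. Women are seen weekly, and Section 4 selects regular attenders. The extra meeting exists to avoid waiting for the next visit, so seven days is closer to the delay it is meant to shorten than to a typical one. This is also a feasibility study meant to find barriers, and a delayed start is one of them.

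Much of this stands. It limits the problem mainly to women who do not attend in person, and it makes seven days an upper illustration rather than an expectation. It does not close the gap, because no text defers randomisation for those women. A barrier can be studied only if its dates are recorded, and none are listed.

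A reader might also infer stronger claims that the documents do not support:

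- **That women are randomised by phone.** Consent and forms may be remote; the place and moment of assignment are not stated.
- **That some women never receive capsules.** This is possible if birth precedes handover, but no frequency is given.
- **That baseline forms follow randomisation, so that GI symptoms are scored with the arm known.** Section 6 places baseline data before randomisation. The paragraph on forms in Section 12 comes later in the text but carries no time marker.
- **That adherence is counted from enrolment.** No denominator is stated.
- **That dropout will be unequal.** The one-arm step makes this a risk, which nothing in the documents quantifies.

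**Conclusion.** The concern holds as a statement about what the plan permits, not about what will happen. An intervention woman can be randomised before she has capsules, with no limit on the wait and no record of its length. For an affected woman, a wait of 3 to 7 days would remove about 14% to 50% of an exposure of 14 to 21 days. Those waits, the start at 37+0 and the birth dates are assumptions, and the number of women affected is unknown. The overall effect on the primary comparison therefore cannot be estimated from the documents, and the power figures show only the direction and rough size of dilution under assumed never-start rates. The firmest consequence is for adherence: as planned, the capsule count cannot separate days without a bottle from missed doses.

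**What to change.** - Keep remote consent and remote baseline forms. Perform the REDCap randomisation, for both arms, only at the contact where a bottle can be handed over, after the baseline forms in the order Section 6 already describes.
- Add the handover date and first-capsule date to the Summary Data Collection Form, and state how they enter the adherence calculation.
- Reconcile Sections 3, 6 and 12 on when capsules begin. The investigators must settle that time; this review does not propose one.
- State whether the 36.0 to 37.6-week window applies to consent, to randomisation, or to both.

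The cost is a wording amendment, a change in when the REDCap assignment is made, and two extra dates per intervention woman. Control women would also need the in-person contact, which runs somewhat against the wish in Section 26 to limit such contact, although weekly visits should usually provide it. A few consented women with no in-person contact before labour would not be randomised. That is preferable to randomising them without access to the intervention or losing them from one arm.

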Colonized pregnant women can pass GBS to their neonates during vaginal birth, putting the neonate at risk for Early Onset *Group B Streptococcus* Disease (EOGBSD), which is associated with a neonatal mortality rate of 5-10%. Prevention of EOGBSD is an ongoing challenge for health professionals involved in perinatal care. The Centers for Disease Control and Prevention (CDC) 2010 guidelines updated by American College of Obstetricians and Gynecologists (ACOG, 2019) require universal antepartum GBS screening and Intrapartum Antibiotic Prophylaxis (IAP) for GBS positive women. While use of these guidelines has significantly reduced the incidence of EOGBSD, up to 30% of laboring women and their fetuses are exposed to IAP. Comorbidities associated with IAP exposure for both the mother (increased incidence of antibiotic resistance, allergic sensitization, diarrhea including *Clostridium difficile*, and fungal infections), and the neonate (*Escherichia coli* infections and greater risk of allergic sensitivity) are significant

Page 5 of 31 Version Date: 12/2/2021

problems. In an attempt to avoid the comorbid problems associated with the current use of IAP during labor, the proposed study will test a low cost, safe, innovative approach to reduce prenatal colonization with GBS while adhering to the CDC prevention guidelines. We hypothesize that women who are GBS positive at 36 weeks gestation and ingest a daily oral prenatal combination probiotic (Florajen DigestionTM) until the time of birth will experience a reduction in GBS colonization.

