Outcome Variables	Study Data Collection Research staff will document data from all measures on the Summary Data Collection Form.	T1 Baseline 36-37 ^{6/7}	T2 Admission to L&D	T3 Postpartum Day 0-14	T4 2 weeks postpartum	T5 6 weeks postpartum
	Procedures					
Qualitative GBS Colonization (+ or -)	Vaginal-rectal GBS swab.		X			
Intervention Adherence [Probiotic group only]	Final Capsule Count			X		
Maternal GI Symptoms	Antepartum Gastrointestinal Symptom Assessment (AP-GI-SA-10)	Х		Х		

Version Date: 12/2/2021

Adverse Events	Adverse Event Solicitation and Documentation Form [Prenatal providers will also solicit for adverse events at all prenatal visits between study visits]		X	X	X
Demo- graphics	Demographic Questionnaire	X			
Lifestyle practices: sexual, hygiene, diet	Questionnaire for Participants	X	X		
Future Feasibility Form					X

Version Date: 12/2/2021

Timeline for Completion of the Project

Timeline for Completion	on of the froject
June 2020	-IRB submission -Planning for meetings with division partners (nursing, medical assistants, midwives, OBs, lab) -Create recruitment tools, handouts, posters -Complete translation of all study materials into Spanish -Upload all final questionnaires into the UNM REDCap system, study projectEstablish safe storage procedures for probiotics prior to distribution to participants -Request probiotic shipment from Florajen
July/August 2020	-Work with research staff and clinical partners on protocols for the 2nd GBS swab collection at T2 -Establish protocols for testing and billing of T2 study swabs with UNM Tricore lab -Receive probiotics from Florajen -Orient research staff to project & create parameters for EHR use for tracking patients -Present study at division meetings of partners (residents, clinic staff, faculty, L&D staff, lab) -Receive iPads from Marquette and add data collection forms to the UNM REDCap system.
September 2020	Start recruitment and data collection
April 2021	End recruitment
May 2021	-Final data collection -Begin data analysis in collaboration with Marquette University
May-September 2021	-Data Analysis -Submit for poster presentation at professional conference(s)
Fall 2021	-Grand Rounds Presentation -Development of poster presentation -Write a paper and submit for publication in peer reviewed journal

7. Study Endpoints

Our primary outcome variable is qualitative GBS colonization (positive versus negative), at the time of labor admission.

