At the time of labor admission to Labor and Delivery, participants will receive a vaginal-rectal GBS swab as a part of the research study. This is not standard of care and thus participants will receive this in addition to the standard of care. The results of the GBS swab will be collected for study purposes only.

All participants regardless of group assignment will receive the usual standard of care for GBS positive status and will be given intrapartum antibiotic prophylaxis (IAP) per protocol during labor.

All participants on postpartum day 0-14, in the hospital will answer these questionnaires: Antepartum Gastrointestinal Symptom Assessment (AP-GI-SA-10), Adverse Event Solicitation and Documentation Form (only for themselves, not their newborn(s)) and Questionnaire for Participants.

*we will not collect Adverse Event Solicitation and Documentation during this study time point because if the information is collected on postpartum day 0, there would be no way of reporting an adverse event for the newborn(s) at this time.

For the intervention group on postpartum day 0-14, study staff will conduct a final capsule count.

All participants at their 2 weeks postpartum visit will have an Adverse Event Solicitation and Documentation Form completed which will also include Adverse Event Solicitation and Documentation for their newborn(s).

Page 17 of 31 Version Date: 12/2/2021

All participants at their 6 weeks postpartum visit will have an Adverse Event Solicitation and Documentation Form & Future Feasibility Form completed which will also include Adverse Event Solicitation and Documentation for their newborn(s).

13. Data Analysis

Demographic characteristics for the full sample and each group will be presented. Logistic regression will be used to identify if the group assignments have relationships to variables such as demographic characteristics, hygiene practices, adherence, and birth characteristics. Logistic regressions test if any of these variables can predict the group that the participants were in. Another advantage of logistic regression is that by adding all the predictors at the same time, we can state the effect of each one controlling for the other predictors, presenting a stronger test of group independence.

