Privacy concerns are taken into account with every patient seen at the UNM. Participants approached and/or interviewed in the clinic setting will be in private offices or examination rooms in the UNM clinics, First Choice Community, or Maternity and Family Planning Clinics Healthcare clinics, where all staff, including research staff, are well-versed in sensitive health care discussions and procedures. Telephone interviews for recruitment and study data gathering are conducted in the research staff area or private physician offices, where all staff have received CITI Training. The office area designated for the entire research staff is isolated from the clinical administrative staff area, providing protection for participants and potential participants during screening, recruitment, study-designated calls, and data entry.

All study sheets used to collect patient information will contain limited data.

At all times throughout the clinical investigation confidentiality will be observed by all parties involved. All data will be secured against unauthorized access. Privacy and confidentiality of information about each subject will be preserved in study reports and in any publication. Each subject participating in this study will be assigned a unique identifier. HIPAA authorization is within the consent. All documents containing personal health information (screening logs, consent documents, data forms) are maintained in locked file cabinets with access available only to research staff and investigators. Data is entered into a password-

Page 23 of 31 Version Date: 12/2/2021

protected system. No individual identifiers are entered into the system. The sole link with personal information is maintained by the research team on a password protected computer on a secure UNM OBGYN department server with access limited to authorized research staff and investigators.

22. Economic Burden to Subjects

	Number of	Responsible Party		
Research Procedures	Samples/Procedures	Study	3 rd Party Payer	
	Sumpres, 11000uu es		or Participant	
Probiotics (intervention group only)	30			
Intervention Adherence- pill count	1			
Antepartum Gastrointestinal Symptom	2			
Assessment (AP-GI-SA-10)				
Adverse Event Solicitation and	3	\square		
Documentation Form				
Demographic Questionnaire	1			
Questionnaire for Participants	2			
Vaginal-rectal GBS swabs	1			
Future Feasibility Form	1			
	Number of	Resp	onsible Party	

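### No GI symptom score is taken while capsules are being taken, so the T1-to-T3 change cannot be shown to measure the probiotic's effect in pregnancy

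*Combined protocol and SAP*

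**What the plan says.** Section 12 sets the baseline score: "All participants will complete baseline forms: Antepartum Gastrointestinal Symptom Assessment (AP-GI-SA-10), Demographic Questionnaire and the Questionnaire for Participants". It sets the only repeat after birth: "All participants on postpartum day 0-14, in the hospital will answer these questionnaires", with the AP-GI-SA-10 first on the list. The schedule table in Section 6 marks the form at T1 and T3 only, and Section 22 budgets two administrations.

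Sections 6 and 12 have the intervention arm take a daily capsule up to birth. Section 12 plans IAP in labor for all participants in both arms. Section 2 lists what the protocol attributes to that exposure: "Comorbidities associated with IAP exposure for both the mother (increased incidence of antibiotic resistance, allergic sensitization, diarrhea" and further items.

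Section 2 also says that the tool was adapted to pregnancy-related GI symptoms after five of the ten women on probiotic in the pilot volunteered that their constipation had eased. Section 13 analyses GI symptoms with a latent change score model and tests the group difference in mean change. Section 7 ends its list of secondary outcomes with "symptoms, and maternal and infant adverse events, at the 6 week postpartum visit", but the form is not scheduled at that visit.

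**The concern.** The interest is in whether the probiotic eases GI symptoms of late pregnancy. The plan has a score from before the first capsule and a score from after the last one, with nothing between. At T3 three things have changed together: the pregnancy is over, the product has been stopped for up to 14 days, and antibiotics with a known GI effect have been given.

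The T3 definition is also loose. Section 12 places it in the hospital but lets it run to day 14, where it meets T4 at two weeks. One woman may therefore be scored hours after her last capsule and another two weeks after.

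At stake is what a small or absent difference would mean. This pilot is meant to inform a larger trial, and a null GI result could be no effect, an effect that faded after the capsules stopped, or an effect masked by birth and antibiotics. The planned scores cannot tell these apart.

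**Working it through.** **1. Number of scores.** The schedule table marks T1 and T3, so 1 + 1 = 2. Section 22 also gives 2, so the plan's own figure is reproduced.

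**2. Order of events.** T1 and randomization (36.0-37.6 weeks), then daily capsules, then labor with planned IAP, birth and end of capsules, then T3 (day 0-14). Of the two scores, one is baseline and one follows birth: 2 - 1 - 1 = 0 scores during capsule use.

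**3. What the planned contrast estimates.** Let b be the average shift in score due to birth and IAP, and e the probiotic effect still visible at T3. The mean change is b + e in the probiotic arm and b in the control arm. The difference is (b + e) - b = e. If b is the same on average in both arms, it cancels. It does not cancel from the change within one arm, and variation in it between women adds to the SD of change. The quantity estimated is e at T3, not the effect during capsule use.

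**4. How much of T3 could still refer to pregnancy.** The documents give no recall period, so R days is assumed. For a form completed on postpartum day d, with all days weighted equally, the share of the window before birth is max(0, R - d)/R. Examples for R = 7:
- days 0-2: (7 + 6 + 5)/(3 × 7) = 18/21 = 86%
- evenly over days 0-14: (7 + 6 + ... + 1)/(15 × 7) = 28/105 = 27%

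| Assumed recall | Days 0-2 | Evenly over days 0-14 | Day 14 |
|---|---|---|---|
| Current symptoms | 0% | 0% | 0% |
| 1 day | 33% | 7% | 0% |
| 7 days | 86% | 27% | 0% |
| 14 days | 93% | 50% | 0% |
| 30 days | 97% | 77% | 53% |

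Days 0-2 stand in for a hospital stay, whose length is not stated. The longer windows need care: a woman enrolled at 37 weeks 6 days who gives birth at 39 weeks 0 days has 273 - 265 = 8 days on product. A 14- or 30-day recall would then reach back before her first capsule, so the share before birth overstates the share on product.

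**5. Illustration only.** Section 5 enrolls up to 75 with 30% dropout: 75 × 0.70 = 52.5, consistent with its figure of about 50 completers. Take 52, or 26 per arm if allocation is equal. Assume a true on-treatment effect of 0.8 SD that shrinks in proportion to the share s. At two-sided 0.05, power is about Φ(0.8 × s × √(26/2) - 1.96):
- s = 1: 82%
- s = 0.86: 70%
- s = 0.50: 30%
- s = 0.27: 12%

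The documents give no effect size, SD or power for GI symptoms. These values show the direction and sensitivity, not an expected loss.

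**The case against.** A reader might infer that the T1-to-T3 change does not measure the probiotic's effect in pregnancy at all, that birth and antibiotics bias it, or that a null would be uninterpretable. The documents do not support these readings.

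- **Recall.** The form is not reproduced. Its name begins with the word antepartum, and the T3 version may already ask about the last days of pregnancy. This stands: the defensible statement is that the change cannot be shown to measure the effect in pregnancy.
- **Bias.** The test is a randomized difference, and birth and planned IAP are common to both arms. Section 6 records the IAP actually given, and Section 13 may adjust for birth characteristics. This also stands: the problem is dilution and noise, not bias from these causes alone.
- **Importance.** GI symptoms are an exploratory secondary outcome in an open-label pilot with about 50 completers, and any result would be imprecise. True, but imprecision does not excuse a schedule that can yield a mostly off-product score.
- **Evidence of a benefit to lose.** The pilot's constipation reports were anecdotes, not a measured effect. This stands.
- **Wording of Sections 7 and 12.** The six-week phrase may attach to adverse events only. Section 6 gives T3 without a place, and Section 16 allows phone or clinic completion. These are points to reconcile, not proof that the measurement is wrong.

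**Conclusion.** The point holds in a limited form. By the stated schedule, no GI score is taken on treatment, and the planned comparison rests on one score taken after birth, after the capsules stop and after planned IAP, anywhere from day 0 to day 14. The randomized difference is not biased by birth or IAP as such, but it estimates what remains of the effect at T3.

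The size of the dilution cannot be fixed from the documents. It depends on the recall period and the day of completion, and any carry-over of the effect after birth would reduce it. With recall of 7 days or less, the share of the T3 window before birth runs from 0% to about 86%. Longer recall can raise it, at the price of reaching back before the first capsule for some women. This calls for an inexpensive improvement to a secondary outcome; it does not make the GI comparison worthless.

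**What to change.** 1. Add one AP-GI-SA-10 before birth, at a late prenatal visit that already takes place. Section 12 describes attendance on a "weekly basis in late pregnancy, generally we anticipate that participants will receive the probiotic at enrollment". Section 16 already provides for entry by iPad, in clinic or by phone. The count in Section 22 goes from 2 to 3.
2. In Section 13, name the last pre-labor score as the GI follow-up in the change model, keep T3 as a secondary time point, and say how women without a pre-labor score are handled.
3. If T3 must stay the only follow-up, word the form for the last week before labor and narrow the window to the hospital stay. In either case, state the recall period.
4. Make Section 7, the schedule table and Section 12 give the same time point for GI symptoms, and settle the conflict between the hospital setting and the day 0-14 window.

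**Cost:** a little more questionnaire and staff work across several clinics, time on product that varies at the last pre-labor score, and no such score for women who deliver soon after T1. The added score is self-reported by unblinded women, as T3 already is. Keeping it to one form limits repeated symptom prompting.
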